5.3.5 Withdrawal of Consent for Study Participation

The infant's parents or legal guardians may withdraw consent voluntarily from participation in the study at any time. The infant's parent or legal guardian is not obligated to state the reason for withdrawal. The reasons for withdrawal, or failure to provide a reason, must be documented by the investigator on the completion/withdrawal section of the electronic case report form (eCRF).

Following withdrawal of consent, no study procedures or collection of data may occur.

5.3.6 Disease Progression Unmasking

Infants enrolled in the treated arms who are determined by the treating physician to have progressive disease will be unmasked and:

- If on 0.25% timolol maleate GFS they will receive open label 0.5% timolol GFS two times a day.
- If on 0.5% timolol maleate GFS the investigator may choose to continue study treatment with 0.5% open label, or withdraw the infant from the Treatment Phase and proceed directly into the 7 day safety follow-up period. Participants may receive alternate therapies during the safety follow-up period.

Infants that are unmasked and receive open label 0.5% timolol maleate GFS will continue to be photographed and followed per the schedule of study procedures (Table 6-1).

5.3.7 Randomization of Participants in the Non-intervention Arm

If at any time during the study the parents of an infant in the non-intervention arm change their mind and want timolol maleate GFS therapy, the infant will be randomized for participation in the study if there is a need for additional enrolled subjects and the infant meets the inclusion criteria and none of the exclusion criteria at the time of first dose.

5.3.8 Termination of Study

This study may be terminated at any time by FDA, NIH, the Investigational New Drug (IND) application sponsor, or upon recommendation by the Data Monitoring Committee (DMC).

6 STUDY PROCEDURES

6.1 Summary of Procedures

Table 6-1: Schedule of Study Procedures

Time (Day)*	Screen/ Baseline	Treatment phase							
	0 ¹ Visit #00/ Visit #01 ⁸	30 (±5 days) Visit #02	60 (± 5 days) Visit #03	90 (± 5 days) Phone contact Visit #04	120 (± 5 days) Visit #05	150 (± 5 days) Phone contact Visit #06	180 (± 5 days) Visit #07	Day 7 (+ 5 days) Phone contact post 180 day study period or early withdrawal Visit #08	Day 270 (± 5 days) Phone contact Confirm ongoing therapy Visit #09
Informed consent	X								
Demographics	X								
Randomization	X								
Vitals: HR, BP ¹⁰	X ⁸	X	X		X		X		
Physical Exam of lesion ²	X	X	X		X		X		
Photograph of lesion	X	X	X		X		X		
Medical History	X								
Physical Exam (systems assessment) ⁹	X	X	X		X		X		
Actual Weight	X	X	X		X		X		
Study Drug Dispensation	X	X	X		X				
Review of Participant Diary (Treatment Administration Info)	X	X	X		X		X		
SOC Timolol Dosing Info (from Phone Script/Follow-up Diary)								X	X
Concomitant Medications	X	X	X	X	X	X	X	X	
Adverse Events	X ^{4,8}	X	X	X	X	X	X	X	X ³
Blood sampling ⁵	X	X	X		X		X		
Parent reported QOL Survey ⁷	X		X				X		
Hemangioma Dynamic Complication Scale ⁶	X	X	X		X		X		
Assessment for treatment failure		X	X		X		X		

¹ Refers to time point prior to start of study drug and may be the same calendar date as day 1.

² This includes treating physician's assessment by Visual Analog Scale (VAS) and measure of width and

thickness. Note: VAS should only be performed at visits 02, 03, 05, 07 and unmasking.

³AEs of special interest will include bradycardia, hypotension, new alteration in mental status, new local skin irritation, new sleep disturbance, apnea, bronchospasm, hypoglycemia, and diarrhea.

⁴AEs will be collected following initial study-specific procedure (e.g., screening, blood draws, dosing)

⁵For infants who are enrolled into the PK portion of the study; up to 3 samples will be obtained throughout the study period and at least one sample should be collected within 2 hours of dosing. Clinic visits for infants in the PK portion of the study will be scheduled to fall within the appropriate time period. Blood pressure and heart rate must be collected within 15 minutes before or after sample collection.

⁶The Hemangioma Dynamic Complication Scale must be collected for all participants.

⁷The parent-reported QOL survey is not required for non-English speaking parents.

⁸OUTPATIENT: When possible the participant should remain in clinic for 2 hours after the first application of timolol in order to monitor for heart rate and BP at 1 hour (+/-15 mins) and 2 hours (+/- 15 mins) after first application. The site PI must also monitor for signs of bradycardia, bronchospasm and hypoglycemia.

INPATIENT: All inpatients will be monitored for the first 24 hours for any signs of bradycardia or any other SAEs of special interest. Hospital staff must also monitor BP and HR 1 and 2 hours after the first administration of timolol.

⁹If performed per local standard of care (SOC)

¹⁰ Blood Pressure Measurement should include systolic and diastolic measurements

*All visits (except for Day 7 post 180 days study period or early withdrawal) can occur within a 5 day window (± 5 days). Day 7 post 180 day study period or early withdrawal must occur within a +5 day window (+5 days).

6.2 Screening/Rescreening

Infants 0-84 days postnatal age with IH will be screened for eligibility.

A participant may be rescreened if there is a transient disease status (e.g., parent/guardian reports a "cold or fever" and met a temporary delaying enrollment criterion of acute illness or fever). No participant may be screened more than twice due to a screening failure result.

6.3 Enrollment/Baseline

Research staff will obtain informed consent from the parent/guardian for all participants who satisfy eligibility criteria.

Once the informed consent has been obtained the following information will be recorded in the CRF:

1. Infant demographics, including birth weight and gestational age at birth and postnatal age.
2. Medical history (birth history and cardiac or pulmonary diagnoses)
3. Physical examination, including weight, height/length, baseline blood pressure, heart rate. Note, at the Baseline Visit, blood pressure* and heart rate must be at 1 hour and 2 hours after the first application of timolol.
4. Photographs and measurements of the IH. Collection of data on the clinical characteristics and measurement of width and thickness of the target hemangioma.
5. Adverse events following initial study-specific procedure (see Table 6-1)
6. Hemangioma Dynamic Complication Scale
7. Parental Hemangioma Quality of Life (QoL) screen
8. Concomitant Medications

* The preferred method of blood pressure collection is auscultation (i.e. manual), however, blood pressure may be collected via machine. Whichever method is used at visit #01 (baseline) should be used at all subsequent visits. Blood pressure measurements should include systolic and diastolic pressure measurements.

6.4 Treatment Period

6.4.1 Randomized Cohort

For those randomized to one of the two treatment arms the study drug Treatment period will include days 1 to 180 days for all infants.

Hospitalized infants who are enrolled in the study will be monitored for the first 24 hours for any signs of bradycardia or any other AEs or AEs of special interest. Hospital staff must also monitor heart rate and blood pressure at 1 and 2 hours (+/- 15 minutes) after the first application of timolol.

Data from a minimum of 25 outpatient infants remaining in clinic after initial application must be collected. Parents of all outpatient infants enrolled in one of the treatment arms will be requested to remain in or close to the clinic for a period of 2 hours after the initial application of timolol. Vital signs (heart rate and blood pressure) will be collected at 1(+/-15 mins) and 2 hours (+/-15 mins) after the first application of timolol. The infant will be monitored for signs and symptoms of an AE or AE of special interest during this period, particularly bronchospasm, arrhythmias, and hypoglycemia .

Thereafter, all infants enrolled in one of the treatment arms will have follow-up office visits at day 30±5 days, 60±5 days, 120±5 days, and 180±5 days and follow-up phone calls at day 90±5 days, 150±5 days. Participants will be monitored by their parent/caregiver as instructed in the patient diary. For parents who have agreed to the PK portion of the study, at least one visit should be scheduled to occur within 2 hours of study drug administration when possible.

Parents will be instructed to administer the study medication immediately after or soon after feeding to avoid hypoglycemia. For each participant, the first application of topical timolol will be applied by the site study team (Site PI or designee).

During the office visits, the following procedures will be performed as specified in Table 6-1:

1. Physical examination, including weight, blood pressure, heart rate.
2. Photographs and measurements of the IH. Collection of data on the clinical characteristics, measurement of width and thickness of the target hemangioma, and color and volumetric size VAS assessments.
3. Hemangioma Dynamic Complication Scale
4. Adverse events/ solicitation of AEs of special interest
5. Parent Hemangioma QoL screen
6. PK sampling (see 6.8) for infants whose parents have consented to this portion of the study (optional). PK sampling will not be collected during the unmasking visit.
7. Concomitant medications
8. Timolol dosing log (to record dose, timing)
9. Weighing of the timolol bottle to verify compliance

During the phone calls, solicitation of concomitant medications and assessment of adverse events will be conducted and documented.

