In contrast to the few documented AEs in the above studies, investigators documented episodic bradycardia in 4 of 22 infants who received Holter monitoring concomitant with timolol therapy for IH.²⁴ Two of these infants with clinically significant bradycardia had weights <2500 g at the initiation of therapy, both were <40 weeks postmenstrual age (PMA) at drug initiation, and both were receiving a timolol dose higher than most of the cohort.²⁴ In a case report of an infant treated with ophthalmic timolol and anti-glaucoma medications, the infant developed altered mental status, hypotonia, hypothermia, bradycardia, apnea, hypotension, and bronch- obstruction, and required intensive care.²⁵ A second case report documented apneic spells in a 2-week-old premature infant who was receiving timolol therapy for glaucoma.²⁶ Apneic spells ceased after discontinuation of timolol.²⁶ In the randomized trial that supported use of intraocular timolol maleate gel-forming solution (GFS) in children with glaucoma, 3 of 72 subjects (4%) developed bradycardia or hypotension.²⁷

Pharmacokinetics of topical application of timolol for IH: Information regarding the PK of topical timolol in children is limited. Studies in adults with intraocular application have indicated systemic absorption of up to 80% of each drop of 0.5% timolol solution.²⁸ In a limited PK study (5 pediatric subjects) of intraocular application of 0.5% timolol solution, plasma timolol concentrations ranged from 3.5 ng/mL in a 5-year-old to 34 ng/mL in a 3-week-old.²⁹ Although the GFS form of timolol is thought to have lower systemic absorption compared to the solution, the likelihood of transcutaneous absorption is potentially increased when timolol is applied to the highly vascularized or ulcerated tissue of IH, or in the presence of occlusion (e.g., diaper hemangiomas).¹² Moreover, compromised barrier function of preterm infant skin and smaller volume of distribution relative to adults may lead to increased systemic absorption when compared to adults.¹² Previous investigators measured plasma concentrations of timolol 30 minutes after applying timolol solution to occluded skin over IH after treatment with fractionated CO₂ laser.³⁰ Timolol concentrations were below the limit of detection (20 pg/mL) in all 9 infants. An additional small study demonstrated absorption in all patients sampled (average of 0.18 ng/dL), but the biologic significance of this is unknown.³¹

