Preliminary data on safety and outcomes of infants treated with topical timolol: The Hemangioma Investigator Group (HIG) conducted a retrospective, multicenter cohort study of topical timolol (applied directly to the hemangioma) solution for IH.³² This study included 738 infants from 9 pediatric dermatology and vascular anomalies centers, thereby demonstrating the wide off-label use of topical timolol for IH. The majority of infants were prescribed timolol in the outpatient setting and none of these received prolonged monitoring. During the active growth phase (0-3 months of age) 51% of infants showed improvement after 3 months of therapy and 82% after 6-9 months of therapy. AEs were rare, occurring in 3.4% of infants and there were no serious adverse events (SAEs).³² There were no serious cardiovascular adverse events.

Univariate and multivariate mixed-effects models showed that only initial IH thickness significantly predicted early improvement in size ($p = 0.0003$) and color ($p = 0.0001$ with IH <1 mm responding more quickly than IH 1-3 mm or >3 mm). The difference in response lost significance with longer duration of treatment, which may reflect natural involution of thicker lesions. While rebound growth with discontinuation of propranolol is well-recognized, optimal treatment duration for topical therapy to prevent rebound upon discontinuation has not been determined

Preliminary data collection on pharmacokinetics of topical timolol: Through the PTN study entitled “Pharmacokinetics of Understudied Drugs Administered to Children Per Standard of Care (NICHD-2011-POP01),” PK evaluation of topical timolol in premature infants with IH is ongoing. Preliminary serum levels in our PTN sponsored study range from 0.03-66.4 ng/ml with a median of 1 (standard deviation 13.0) ng/ml. None of the infants in this cohort had signs or symptoms of beta blockade or adverse events from timolol.

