2.3.1.2 Risks of topical timolol therapy

Transcutaneous absorption of topical timolol solution has not been extensively studied in adults or children. Application of topical timolol to highly vascularized or ulcerated tissue of infantile hemangiomas or under occlusion (e.g. diaper hemangiomas) may increase transcutaneous absorption, and pose a greater risk of adverse events associated with systemic beta-blockers. Effects of systemic beta blockade include bronchial hyperreactivity, hypotension, bradycardia, hypoglycemia, sleep disturbance, hypothermia, and changes in extremity color or temperature e.g., coldness. Infants with known baseline risk factors for bradycardia, hypoglycemia, or bronchial hyperreactivity will be excluded from enrollment according to the protocol's predefined

criteria. More specific to the topical application of timolol, irritation or dermatitis may occur.

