4 STUDY DESIGN

4.1 Study Design

This is a prospective, multi-center, double-masked, randomized, efficacy, safety, and PK study. Infants who satisfy all eligibility criteria will be randomized (1:1) to 0.25% or 0.5% timolol GFS and will be treated for a period of 180 days (Figure 1).

Randomization will be stratified using two age groups: <4 weeks postnatal age and ≥4 weeks postnatal age. Infantile hemangiomas are more common in preterm and low birth weight infants, therefore, it is expected that 10% of enrolled subjects will be preterm infants. Infants who are eligible for the study based on inclusion and exclusion criteria but whose parents decline treatment of the hemangioma will constitute the non-intervention arm of the study and will serve as a control group.

Infants who have progressive disease and require additional therapy as determined by the treating physician will be unmasked: if on the 0.25% timolol maleate GFS they will receive open label 0.5% timolol GFS two times a day and continue to be followed per the schedule of study procedures (Table 6-1). If they are on 0.5% the investigator may choose to continue the 0.5% open label or withdraw the participants from the Treatment Phase and proceed into the safety follow-up period and receive alternate therapies.

This study will be conducted in accordance with current U.S. Food and Drug Administration regulations and guidelines, (or, as applicable, international regulations and associated guidelines), the International Council for Harmonisation Guidelines on Good Clinical Practice (which incorporate the principles of the Declaration of Helsinki), as well as all other applicable national and local laws and regulations.

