5 STUDY POPULATION

5.1 Selection of the Study Population

Young infants with superficial small hemangiomas in the proliferative phase and who have been identified by their treating physician as needing topical treatment with timolol maleate GFS will be considered for the study. For infants with more than one lesion, a target lesion (a lesion that will require treatment with study drug) will be identified. The infants will be administered study drug only on that lesion. Infants who are eligible for the study based on inclusion and exclusion criteria but whose parents decline treatment with timolol will be included in the non-intervention (control group) in the study.

The majority of recruitment is anticipated to be from outpatient pediatric dermatology clinics, but additional recruitment may occur from inpatient units including the newborn nursery and neonatal intensive care units.

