5.2.2 Exclusion Criteria

1. History of previous treatment with any pharmacologic or laser therapy for IH
2. Ongoing therapy with an oral beta blocker or oral corticosteroid (e.g., cardiac arrhythmia, adrenal insufficiency, upper airway obstruction, tetralogy of fallot, hypertension, reactive airways disease)
3. IH that requires systemic therapy (defined by dynamic complication scale >3)
4. Infants with more than one hemangioma that requires therapy
5. IH of the non-keratinized mucosa
6. Hemodynamically significant cardiovascular disease, as determined by the investigator
7. Known allergy to beta blockers or vehicle
8. Heart rate <100 beats per minute at screening visit
9. Known prenatal or postnatal diagnosis of 2nd/3rd degree atrioventricular block
10. History of reactive airway disease (RAD)
11. Any condition which would make the participant, in the opinion of the investigator, unsuitable for the study

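### The protocol contradicts itself on whether outpatients must have heart rate and blood pressure taken 1 and 2 hours after the first dose, and it makes no firm provision for infants under 2500 g or under 40 weeks PMA

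*Combined protocol and SAP*

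**What the plan says.** Four places in the protocol deal with the first-dose check in outpatients, and they do not agree.

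- Section 6.3 states, as a requirement and with no outpatient exception, that baseline-visit blood pressure and heart rate be taken 1 and 2 hours after the first application.
- Table 6-1, footnote 8, asks outpatients to stay 2 hours if that is possible. It also obliges the site PI to watch for signs of bradycardia, bronchospasm and hypoglycemia.
- Section 6.4.1 says parents of all treated outpatients will be asked to stay in or near the clinic, and sets a floor: "Data from a minimum of 25 outpatient infants remaining in clinic after initial application must be collected".
- Section 8.1 applies the 1- and 2-hour readings to outpatients whose parents agree to stay and are able to.

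For inpatients, footnote 8 and 6.4.1 make the two readings mandatory, on top of 24 hours of monitoring.

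On risk, section 2.1 reports episodic bradycardia in 4 of 22 Holter-monitored infants. It continues: "Two of these infants with clinically significant bradycardia had weights <2500 g at the initiation of therapy, both were <40 weeks postmenstrual age (PMA"), and adds that both were on a higher dose than most of that cohort. It also warns that "compromised barrier function of preterm infant skin and smaller volume of distribution relative to adults may lead to increased systemic absorption".

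On eligibility, section 5.2.1 admits infants aged 0 to 84 days. Section 5.2.2 has no weight, gestational-age or PMA limit. Its nearest specific criteria are "Heart rate <100 beats per minute at screening visit", atrioventricular block and significant cardiovascular disease; criterion 11 leaves the rest to the investigator. Section 4.1 says "it is expected that 10% of enrolled subjects will be preterm infants", and section 5.1 says "The majority of recruitment is anticipated to be from outpatient pediatric dermatology clinics".

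**The concern.** A site cannot tell from the protocol whether an outpatient may leave before the two readings. If it follows 6.3, every treated infant is measured. If it follows the other three places, any outpatient may leave, including one with the features that section 2.1 reports in its two cases. The floor of 25 is a trial total and protects no particular infant.

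For an infant who leaves, the next scheduled heart rate and blood pressure are at Day 30 (±5 days), unless optional PK sampling happens to bring an earlier reading. Until then, detection rests on the parents and the diary, and bradycardia or hypotension without symptoms could go unseen. The dose is one drop whatever the infant's weight, so the smallest infants receive the most per kilogram.

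The protocol requires the check for inpatients and gives no reason why an equally small infant seen in clinic may go without it.

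**Working it through.** **1. Can infants with both features enter as outpatients?** PMA is gestational age plus postnatal age. An infant born at 32 weeks reaches 40 weeks PMA at (40 − 32) × 7 = 56 days, well inside the 84-day limit. One born at 37 weeks is under 40 weeks PMA for the first (40 − 37) × 7 = 21 days. Nothing specific in 5.2.2 removes a healthy infant of this kind, whatever the weight.

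**2. The series in section 2.1.** Episodic bradycardia: 4/22 = 0.182. With p = 4/22, n = 22 and z = 1.96, the 95% Wilson interval is [p + z²/2n ± z√(p(1 − p)/n + z²/4n²)] / (1 + z²/n) = (0.073, 0.385). The section does not say how many of the 22 were small or young, so no rate can be derived for infants with those features.

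**3. Applied dose per kilogram.** Section 7.1 gives 0.25 mg per drop of the 0.5% product.

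| Weight | mg/kg per application |
|---|---|
| 2.0 kg (assumed) | 0.25 / 2.0 = 0.125 |
| 2.5 kg (the cut-off in 2.1) | 0.25 / 2.5 = 0.100 |
| 5.0 kg (assumed) | 0.25 / 5.0 = 0.050 |

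The range from 5.0 kg to 2.0 kg is 0.125 / 0.050 = 2.5-fold. This is dose applied, not absorbed. The dose in the Holter series is not given per kilogram, so the two cannot be compared directly.

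**4. The plan's own detection figures.** Section 10.3 gives probabilities of 0.63 and 0.99 of seeing at least one event among 100 infants at rates of 0.01 and 0.05. Both reproduce: 1 − 0.99^100 = 0.634 and 1 − 0.95^100 = 0.994. They cover events over all treated infants and stand. For a finding that only a timed first-dose reading would show, with just 25 infants measured, the same formula gives 1 − 0.99^25 = 0.222 and 1 − 0.95^25 = 0.723.

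**5. Coverage of preterm infants at the floor.** Inputs: 100 randomized (10.3), 10% preterm (4.1), 25 measured (6.4.1). Assumptions: all 100 are outpatients, and staying does not depend on prematurity. The number of preterm infants measured is then hypergeometric.

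- Mean measured: 25 × 10/100 = 2.5, so 7.5 of 10 are unmeasured.
- P(none measured) = C(90,25)/C(100,25) = 0.048.
- P(two or fewer) = Σ C(10,k)·C(90,25 − k)/C(100,25) over k = 0, 1, 2 = 0.522.

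| Scenario (assumed) | Preterm outpatients unmeasured, mean |
|---|---|
| 25 measured, 10 preterm outpatients | 7.5 of 10 |
| 50 measured, 10 preterm outpatients | 5.0 of 10 |
| 75 measured, 10 preterm outpatients | 2.5 of 10 |
| 25 of 95 measured, 5 preterm outpatients and 5 inpatients | 5 − 25 × 5/95 = 3.7 of 5 |

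Preterm is only a proxy: some preterm infants will be past both cut-offs at first dose, and some term infants will not.

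**The case against.** The case for leaving the outpatient rule alone has real weight.

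- **Other safeguards exist.** Footnote 8 gives the site PI a duty to watch for bradycardia, parents monitor using the diary, and section 8.5 pauses the trial at two serious adverse reactions. This stands, but none of these guarantees a timed reading for an infant who leaves.
- **The evidence is thin and confounded.** It is two infants, both on a higher dose than most of their cohort, and section 2.1 does not tie the events to the first dose. This stands.
- **The check may miss the hazard.** Two spot readings can miss episodic bradycardia of the kind found on Holter. This reduces the benefit without removing it.
- **Other experience is reassuring.** Of the premature POP01 infants, with levels up to 66.4 ng/ml, section 2.1 says "None of the infants in this cohort had signs or symptoms of beta blockade or adverse events from timolol". The 738-infant cohort had no serious adverse events and no serious cardiovascular events. However, most of that cohort was prescribed timolol as outpatients, without prolonged monitoring, so silent events are not ruled out.
- **Inpatients differ in practice.** They are under staff observation anyway, and the smallest infants may be recruited in hospital. That explains why the check is easier there, not why a small outpatient may go without it.

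Stronger readings are tempting, but the documents do not carry them. A reader might infer that the check is voluntary for every outpatient; section 6.3 says otherwise, so the defect is a contradiction. A reader might compute a 2-in-22 rate of clinically significant bradycardia; section 2.1 does not say that only two infants had it. A reader might conclude that either low weight or low PMA alone carries the risk; both infants had both. And a reader might take section 2.3.1.2 ("Infants with known baseline risk factors for bradycardia, hypoglycemia, or bronchial hyperreactivity will be excluded from enrollment") as a broken promise to exclude preterm infants. That sentence refers to the predefined criteria, which do include cardiac and respiratory exclusions, and it does not name prematurity.

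**Conclusion.** The point holds as an internal contradiction with a modest safety consequence. One place requires the first-dose readings and three make them conditional. Under the conditional wording, an outpatient under 2500 g and under 40 weeks PMA may have no scheduled heart rate or blood pressure between the first application and Day 30.

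How many infants this affects cannot be read from the documents. The 7.5 of 10 is a worst case: it treats the floor as the number measured, although all parents are asked to stay, and it puts every preterm infant in the outpatient group. It is not a forecast. The benefit of the readings is plausible rather than demonstrated.

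I would ask for the change because it is cheap and makes firm a check the protocol already contains. My confidence is medium. No endpoint, sample size or efficacy analysis is affected, and the safety precision figures in section 10.3 are correct.

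**What to change.** Put one rule in section 6.3, Table 6-1 footnote 8, section 6.4.1 and section 8.1:

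- For treated infants, heart rate and blood pressure are taken 1 and 2 hours (±15 minutes) after the first application in all inpatients, and in any outpatient who weighs less than 2500 g or is under 40 weeks PMA on that day.
- If such a family cannot stay, the first application is moved to a day when they can, within the 84-day age limit.
- Other outpatients remain under the current request, with the minimum of 25.

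Requiring either feature rather than both is a precaution that goes beyond section 2.1; the sponsor may justify another cut-off. In section 2.3.1.2, add only a clarification that low weight or low PMA is not itself an exclusion criterion.

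The cost is a 2-hour stay or a second visit for a small number of families, and a few may decline. The documents do not allow that number to be counted: about 0.10 × 100 = 10 preterm infants are expected, not all of whom will qualify or be outpatients, and some term infants enrolled very early would be added. The site team already gives the first application, and the measurements and time windows already exist.
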